**Table 6-6. AMG 340 Dose Modification Guidelines for Adverse Events**

Grade	Description of Severity a	Interruption/Delay	Specific Management	Restart Guidance	Permanent Discontinuation
Cytokine Release Syndrome continued (see Section 6.2.1.6 for additional guidance and grading scale details)					
2	
Symptoms require and respond to moderate intervention
 
 
Feverb: <math>\geq 38^{\circ}\text{C}</math> WITH
 
Hypotension: not requiring vasopressors AND/ORc
 
Hypoxia: requiring low-flow nasal cannulad or blow-by
 
	
Delay AMG 340 until event improves to CRS grade <math>\leq 1</math>.
	
Administer:
 
 
Symptomatic treatment (eg, paracetamol/acetaminophen) for fever
 
Supplemental oxygen when oxygen saturation is <math>< 90\%</math> on room air (low-flow [<math>\leq 6</math> L/minute] nasal cannula or blow-by)
 
IVF when systolic blood pressure is <math>< 85</math> mmHg. Persistent tachycardia (eg, <math>> 120</math> bpm) may also indicate the need for intervention for hypotension.
 
 
Monitor:
 
 
CRS symptoms including temperature, blood pressure, and pulse oximetry
 
Fluid status, maintain IVF as needed
 
Cardiac and other organ function
 
Consider Chest X-Ray and obtaining appropriate cultures to rule out infection
 
 
For subjects with rapid onset (<math>< 4</math> hours from start of infusion), extensive co-morbidities or poor performance status, strong suggestion to manage per grade 3 CRS guidance below.
 
Thrombocytopenia occurring in the setting of CRS can be managed per Section 6.2.1.4 and/or per institutional guidelines.
	
 
The next infusion may be administered if all of the following criteria are met: 
 
If CRS occurred during AMG 340 infusion, infusion has been interrupted for at least 72 hours
 
Resume AMG 340 at same dose or reduce to next lower dose if clinically indicated.
 
The event has resolved to grade <math>\leq 1</math> prior to restarting treatment
 
 
 
	
If there is no improvement to CRS <math>\leq</math> grade 1 within 7 days

Abbreviations and footnotes defined on last page of table.

Page 5 of 19

Table 6-6. AMG 340 Dose Modification Guidelines for Adverse Events

Grade	Description of Severity a	Interruption/ Delay	Specific Management	Restart Guidance	Permanent Discontinuation
Cytokine Release Syndrome continued (see Section 6.2.1.6 for additional guidance and grading scale details)					
3	
Symptoms require and respond to aggressive intervention
 
 
Feverb: <math>\geq 38^{\circ}\text{C}</math> WITH
 
Hypotension: requiring a single vasopressor (excluding vasopressin) AND/ORc
 
Hypoxia: requiring high-flow nasal cannulad, facemask, nonrebreather mask, or Venturi mask
 
	Delay AMG 340 until event improves to CRS grade $\leq 1$ .	
Administer:
 
 
Symptomatic treatment (eg, paracetamol/acetaminophen) for fever
 
Supplemental oxygen (high-flow nasal cannula [<math>> 6 \text{ L/min}</math>], facemask, non-rebreather mask, or Venturi mask), as needed
 
A vasopressor <math>\pm</math> vasopressin, as needed
 
Dexamethasone (or equivalent) IV at a dose maximum of (3 doses of 8 mg [24 mg/d]). The dose should then be reduced step-wise.
 
 
AND/OR
 
 
Consider use of tocilizumab (in countries where available) as an additional therapy in this setting at a dose of 4-8 mg/kg as a single dose. Tocilizumab can be repeated for an additional 3 doses with at least an 8 hour interval between doses
 
	
 
The next infusion may be administered if all of the following criteria are met: 
 
The Amgen medical monitor must be consulted prior to re-starting treatment
 
If CRS occurred during AMG 340 infusion, infusion has been interrupted for at least 72 hours
 
The event has resolved to grade <math>\leq 1</math> prior to re-starting treatment
 
 
 
	
If there is no improvement to CRS <math>\leq</math> grade 2 within 5 days and CRS <math>\leq</math> grade 1 within 7 days.
 
In the case of 2 separate grade 3 CRS events.

Page 6 of 19

Abbreviations and footnotes defined on last page of table.

Table 6-6. AMG 340 Dose Modification Guidelines for Adverse Events

Grade	Description of Severity a	Interruption/ Delay	Specific Management	Restart Guidance	Permanent Discontinuation
Cytokine Release Syndrome continued (see Section 6.2.1.6 for additional guidance and grading scale details)					
			
 
If tocilizumab is not available, siltuximab (an anti-IL-6 monoclonal antibody) may be used in the management of CRS. The recommended dose of siltuximab is 11 mg/kg administered over 1 hour as an intravenous infusion, consistent with the prescribing information for the treatment of multicentric Castleman's disease (SYLVANT® Prescribing Information, 2019), and the CARTOX Working Group Guidelines for CRS management (Neelapu, 2018). Siltuximab may be repeated if needed, in the event that CRS recurs after a subsequent infusion of AMG 340. Siltuximab may not be repeated in an individual subject that develops anaphylaxis to siltuximab, or gastrointestinal perforation after siltuximab.
 
 
Monitor:
 
 
CRS symptoms including temperature, blood pressure, and pulse oximetry
 
Fluid status, maintain IVF as needed
 
Consider Chest X-Ray and obtaining appropriate cultures to rule out infection
 
If refractory hypotension (after 2 fluid boluses), consider ECHO
 
 
Admit to intensive care unit for close clinical and vital sign monitoring per institutional guidelines.
 
Thrombocytopenia occurring in the setting of CRS can be managed per Section 6.2.1.4 and/or per institutional guidelines.
		

Page 7 of 19

Abbreviations and footnotes defined on last page of table.

Table 6-6. AMG 340 Dose Modification Guidelines for Adverse Events

Grade	Description of Severity a	Interruption/ Delay	Specific Management	Restart Guidance	Permanent Discontinuation
Cytokine Release Syndrome continued (see Section 6.2.1.6 for additional guidance and grading scale details)					
4	Life-threatening symptoms • Fever b : $\geq 38^{\circ}\text{C}$ WITH • Hypotension: requiring multiple vasopressors (excluding vasopressin) AND/OR c • Hypoxia: requiring positive pressure (eg, CPAP, BiPAP, intubation, and mechanical ventilation)	N/A	Administer: 
 
Symptomatic treatment (eg, paracetamol/acetaminophen) for fever
 
Supplemental oxygen (positive pressure [eg, CPAP, BiPAP, intubation and mechanical ventilation]), as needed
 
Multiple vasopressors, as needed
 
Dexamethasone (or equivalent) IV at a dose maximum of (3 doses of 8 mg [24 mg/d]). Further corticosteroid use should be discussed with the Amgen medical monitor.
 
Tocilizumab should be administered at a dose of 4-8 mg/kg as a single dose. Tocilizumab can be repeated for an additional 3 doses with at least an 8 hour interval between doses
 
	N/A	Immediately stop the infusion (if applicable) and permanently discontinue AMG 340

Page 8 of 19

Abbreviations and footnotes defined on last page of table.

Table 6-6. AMG 340 Dose Modification Guidelines for Adverse Events

Grade	Description of Severity a	Interruption/ Delay	Specific Management	Restart Guidance	Permanent Discontinuation
Cytokine Release Syndrome continued (see Section 6.2.1.6 for additional guidance and grading scale details)					
			
 
If tocilizumab is not available, siltuximab (an anti-IL-6 monoclonal antibody) may be used in the management of CRS, following the criteria outlined in the Management of Adverse Events table. The recommended dose of siltuximab is 11 mg/kg administered over 1 hour as an intravenous infusion, consistent with the prescribing information for the treatment of multicentric Castleman's disease (SYLVANT® Prescribing Information, 2019), and the CARTOX Working Group Guidelines for CRS management (Neelapu, 2018). Siltuximab may be repeated if needed, in the event that CRS recurs after a subsequent infusion of AMG 340. Siltuximab may not be repeated in an individual subject that develops anaphylaxis to siltuximab, or gastrointestinal perforation after siltuximab.
 
 
Monitor:
 
 
CRS symptoms including temperature, blood pressure, and pulse oximetry
 
Fluid status, maintain IVF as needed
 
Consider Chest X-Ray and obtaining appropriate cultures to rule out infection
 
If refractory hypotension (after 2 fluid boluses), consider ECHO
 
 
Admit to intensive care unit for close clinical and vital sign monitoring per institutional guidelines.
 
Thrombocytopenia occurring in the setting of CRS can be managed per Section 6.2.1.4 and/or per institutional guidelines.
		

Abbreviations and footnotes defined on last page of table.

Page 9 of 19

Table 6-6. AMG 340 Dose Modification Guidelines for Adverse Events

Grade	Description of Severity a	Interruption/ Delay	Specific Management	Restart Guidance	Permanent Discontinuation
Tumor Lysis Syndrome (TLS) – Grading according to Cairo-Bishop Criteria (see Section 11.11)					
2	• Clinical TLS	Immediate interruption/ delay until event has improved to grade $\leq 1$	TLS should be managed according to the local standard of care and institutional guidelines.	
 
• Restart possible if successfully managed and improvement to <math>\leq</math> grade 1 in <math>\leq 14</math> days
 
• In case of infusion interruption, continue treatment with next scheduled infusion, do not resume prior infusion or administer delayed infusion.
 
• Delay of next infusion: 
 
- <math>\leq 72</math> hours: follow the Schedule of Activities for the cycle day on which the infusion was originally planned. The following infusion should then be administered after 7 (<math>\pm 1</math>) days
 
- <math>> 72</math> hours: skip the infusion and resume Schedule of Activities for the next scheduled infusion
 
 
 
• Hospitalization: 40 to 48 hours
 
	N/A
$\geq 3$	• Clinical TLS	N/A	TLS should be managed according to the local standard of care and institutional guidelines	N/A	Immediately stop the infusion (if applicable) and permanently discontinue AMG 340 therapy

Abbreviations and footnotes defined on last page of table.

Page 10 of 19

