#### **6.2.1.2 Dose Priming**

Based on the nonclinical pharmacology of AMG 340, a lower rate of CRS is anticipated than with other T-cell-engaging bispecifics; however, based on the mechanism of action of AMG 340, the most likely DLT to occur is still CRS  $\geq$  grade 3. Cytokine release syndrome will be managed per Principal Investigator discretion and institutional guidelines (a guide for management of CRS is provided in [Table 6-6](#) if institutional guidelines have not been established). Definitions for adverse events, serious adverse events, and DLTs are provided in Section [8.4.6.1.1](#), [8.4.6.1.2](#), and [6.2.1.4.1](#), respectively.

If a grade  $\geq$  3 CRS event occurs in Cohort N (where N represents a Cohort number) during the DLT period, or at the discretion of the DLRT, a dose equal to or less than the dose for Cohort N will be designated as the ‘Priming Dose’ and dose administration in subsequent cohorts (Cohorts N+1 and on) may be modified as follows:

- On Cycle 1 Day 1, subjects will receive the Priming Dose.
- On Cycle 1 Day 8, subjects will receive the full dose corresponding to the cohort in which they have been enrolled.

Note: a second priming dose may be introduced based on emerging data.

If a subject experiences CRS grade  $\geq$  2, or any other grade  $\geq$  2 toxicity after receiving a priming dose that is not unequivocally due to the subject’s underlying malignancy or other extraneous cause, administration of the full dose on cycle 1 day 8 must await approval by the Amgen Medical Monitor(s). At a minimum, CRS must have resolved to

grade  $\leq$  1 before the next is administered. The dose and timing of the full dose for such a subject may be modified at the discretion of the Amgen Medical Monitor and the Investigator; if the subject has their full dose reduced in cycle 1, the subject will be considered DLT-unevaluable and should be replaced. In subsequent cycles, subjects will receive the full dose on day 1.

Following implementation of a priming dose, if administration of the full dose is delayed in cycle 1, the DLT period for that subject should be extended to the same degree (eg, if the full dose is delayed by 4 days, the DLT period will also be extended 4 days). For clarity, treatment-emergent adverse events meeting criteria for a DLT will be treated as a DLT whether they occur after administration of the priming or the full dose.

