- During any cycle, if a subject develops an ANC < 500/ $\mu$ L, platelets < 10,000/ $\mu$ L, or a hemoglobin < 6.5 g/dL, blood samples must be collected every 3 days and study treatment withheld. Treatment may resume when ANC returns to  $\geq$  1,000/ $\mu$ L, platelet counts return to  $\geq$  50,000/ $\mu$ L or baseline platelet count levels (in subjects with baseline platelets < 50,000/ $\mu$ L), or hemoglobin returns to  $\geq$  8.0 g/dL.
- AMG 340 should be discontinued in any subject who experiences CRS, TLS, or a non-hematologic treatment-emergent adverse event that meets DLT equivalent criteria until resolution of the toxicity to  $\leq$  grade 1 or baseline; thereafter study drug may be resumed with one dose level reduction with Medical Monitor approval.

Up to 2 dose reductions are allowed to manage toxicity; thereafter toxicity will be deemed 'unacceptable' and the subject will be discontinued from therapy. Assessment schedules and cycles are fixed and should continue regardless of whether a dose is held.

While investigator discretion should be used for subject management with regards to toxicities, guidelines for management of CRS and NT are provided in [Table 6-6](#) and [Table 6-5](#).

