##### **Infusion Delay due to Technical/Logistical Issues**

If the infusion delay was  $\leq$  7 days, the dose can be administered without specific precautions. Procedures performed will follow the schedule of assessments for the cycle day on which the infusion was originally planned. The following infusion should then be administered after 21 ( $\pm$  1) days (eg, if the day 8 infusion needs to be delayed for logistical issues, and could only be administered on day 10, the next infusion should be administered 21 days later [ $\pm$  1 day]). The  $\pm$  1-day window is allowed until the original dosing schedule is met again.

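### For grade 2 tumor lysis syndrome with a delay of at most 72 hours, Table 6-6 sets the following infusion 7 (±1) days later, which matches no planned dose

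*Protocol*

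**What the plan says.** Table 6-6 (TLS, grade 2, Restart Guidance) allows a restart if the event improves to grade 1 or lower within 14 days. If the next infusion is delayed by at most 72 hours, it is given on the schedule of its original cycle day, and then: "The following infusion should then be administered after 7" (±1) days. If the delay exceeds 72 hours, the infusion is skipped and dosing resumes at the next scheduled one.

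Dosing is once every 3 weeks in 21-day cycles (Protocol 1.1, Treatments; Table 6-1). With priming, cycle 1 has a priming dose on day 1, possibly a second on day 5, and the full dose on day 8. Section 6.2.1.2 adds: "In subsequent cycles, subjects will receive the full dose on day 1". Section 8.1.2 schedules all later doses from day 1, and Section 6.2.1.4 keeps cycles fixed when a dose is held.

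If a full dose in cycle 1 is late, Section 6.2.1.2 says "the DLT period for that subject should be extended to the same degree". SAP 5.1.1 counts a DLT only if it starts within 21 days of the first dose.

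**The concern.** A 7-day interval suits weekly dosing, and this trial has no weekly schedule. A site that follows the row literally would give a dose the protocol does not plan, and would give it early, to a subject who has just recovered from clinical TLS. The row does not say what then happens to the planned day 1 dose. This works against the stated reasons for dosing every 3 weeks, which are to leave time to detect toxicity between doses and to limit accumulation (Protocol 1.1, Study Rationale). In cycle 1 the extra dose would also fall within the period used to judge dose-limiting toxicity, a primary endpoint. The alternative is for the site to disregard an explicit instruction in a safety table.

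**Working it through.** **Inputs**
- Day 1 is the date of the first dose (Section 8.1.2) and a cycle is 21 days, so C2D1 = 1 + 21 = day 22 and C3D1 = 1 + 2×21 = day 43.
- Cycle 1 doses fall on day 1 alone, on days 1 and 8, or on days 1, 5 and 8. Later cycles are dosed on day 1 only (Section 6.2.1.2, Table 6-1). The dosing row of Table 1-1 is broken in the copy available, so the schedule is taken from the text.
- The delay is d = 1, 2 or 3 days (at most 72 hours). The rule's interval is 6–8 days.
- Laboratory TLS, which clinical TLS requires, arises up to 7 days after treatment starts (Section 11.11). Recovery must come within 14 days (Table 6-6), taken here as counted from onset.

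**Step 1: can the 7 days be reproduced?** Nominal gaps between planned doses are 21, 21, … without priming; 7, 14, 21, … with one priming dose; and 4, 3, 14, 21, … with two. The only 7-day gap is C1D1 to C1D8 with a single priming dose. C1D1 is by definition the first dose, so on-treatment TLS cannot have delayed it. The figure is not reproduced for any dose that TLS can delay.

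**Step 2: gap after a delayed dose.** Gap = next planned day − (planned day + d).

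| Delayed dose | Next planned dose | Gap for d = 1, 2, 3 | Within 6–8 days? |
|---|---|---|---|
| C1D5 | C1D8 | 2, 1, 0 | No |
| C1D8 | C2D1 (day 22) | 13, 12, 11 | No |
| C2D1 (day 22) | C3D1 (day 43) | 20, 19, 18 | No |

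Every later day 1 dose repeats the last row.

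**Step 3: which delays can occur?** After a day 1 dose, onset is by day 1 + 7 = 8 and recovery by 8 + 14 = 22. That is C2D1 itself, so no delay of 1–3 days arises. If the 7-day window is counted per dose, the same holds from each later day 1 dose to the next. TLS after a priming dose can hold up C1D8 by 1–3 days. TLS after C1D8 (onset by 8 + 7 = 15, recovery by 15 + 14 = 29) can hold up C2D1, again counting the window per dose. Otherwise a delayed C2D1 needs an atypical course, such as a late clinical complication.

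**Step 4: size**
- *C1D8 given on g = 9, 10 or 11.* The rule gives g + 6 to g + 8, that is days 15–17, 16–18 or 17–19. This is 22 − 19 = 3 to 22 − 15 = 7 days before C2D1. The extended DLT period ends on 21 + (g − 8) = day 22, 23 or 24, so every one of these dates lies inside it. All also lie inside the SAP's 21 days.
- *C2D1 given on days 23–25.* The rule gives 23 + 6 = 29 to 25 + 8 = 33, which is 43 − 33 = 10 to 43 − 29 = 14 days before C3D1.
- *C1D5 given on days 6–8.* The rule gives 6 + 6 = 12 to 8 + 8 = 16, which is 4–8 days after the planned C1D8. Here it slows dosing.

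**Step 5: consistency within the row.** A C2D1 dose delayed by exactly 72 hours is given on day 25 and followed on days 31–33. If the delay is slightly longer, the dose is skipped and the next is C3D1, day 43.

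**The case against.** The strongest reply is that the rule will seldom operate and is fenced in when it does. TLS is a potential concern in Table 2-2, and it is not among the events reported for the 23 dosed subjects in Section 2.2.4.3, although a non-serious grade 2 event could go unlisted there. After a grade 2 or worse toxicity following priming, the C1D8 dose waits for Medical Monitor approval and its dose and timing may change (Section 6.2.1.2). Section 6.2.1.4 adds that "thereafter study drug may be resumed with one dose level reduction with Medical Monitor approval". The DLT consequence also has exits: "if the subject has their full dose reduced in cycle 1, the subject will be considered DLT-unevaluable and should be replaced", and the TLS might itself be called a DLT under Section 6.2.1.6.1.2. All of this stands and limits the size of the point. None of it corrects the date in the table.

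It is also true that the protocol does not treat about 7 days as unsafe in itself. Single priming puts doses 7 days apart, and other Table 6-6 rows give a delayed infusion provided the next scheduled one is more than 6 days away. But those rows refer to a dose already scheduled, and the priming gaps follow a priming dose. The TLS row creates a dose that is not on the schedule. The Part B dosing frequency is still open, but a change of schedule in Part A needs an amendment (Section 4.1.1), and no weekly schedule is described.

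Three stronger readings are tempting, and the documents do not support them:
- *The subject with TLS is redosed 14 days sooner than one with a pump fault.* Section 6.2.2.4 says "The following infusion should then be administered after 21" (±1) days, and 21 − 7 = 14. But that section is a poor yardstick for day 8 doses. Its own example ("eg, if the day 8 infusion needs to be delayed for logistical issues, and could only be administered on day 10") leads to a next dose on days 10 + 20 = 30 to 10 + 22 = 32, which is 8–10 days after C2D1. Against the planned schedule, the C1D8 error is 3–7 days.
- *The extra dose breaches a limit of three doses in the DLT window.* Section 6.2.1.4.1 describes how many doses the first cycle contains. It does not set a cap.
- *C2D1 must wait until the extended DLT period ends.* No section requires this, and fixed cycles and day 1 scheduling point the other way.

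**Conclusion.** The point holds as a wrong interval in a dosing instruction. The 7 (±1)-day sentence fits no planned gap after a dose that TLS can delay, and it disagrees with Sections 6.2.1.2, 6.2.1.4 and 8.1.2. In the main reachable case, a delayed C1D8, it is 3–7 days early. For a delayed C2D1, which is reachable mainly after TLS following C1D8, it is 10–14 days early. Each trigger affects one interval. The DLT consequence applies only to a subject who remains evaluable and whose TLS has not itself been counted as a DLT.

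The conclusion assumes that the text schedule matches the dosing row of Table 1-1. The ranking of cases also assumes that the 7-day TLS window is counted per dose and the 14-day recovery limit from onset. Severity is minor: a wording correction to a safety rule, with no statistical quantity affected.

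**What to change.** Delete the 7-day sentence from the grade 2 TLS row and write instead: *Give the following infusion at the next scheduled dose in the Schedule of Activities (day 1 of the next cycle); for a delayed cycle 1 step dose, follow Section 6.2.1.2.*

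The next dose then comes 11–13 days after a delayed C1D8 dose and 18–20 days after a delayed day 1 dose. This agrees with Sections 6.2.1.2, 6.2.1.4 and 8.1.2, and with the rule for longer delays in the same row. The cost is one sentence in a protocol amendment; sample size, data collection and SAP analyses are unchanged.

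The day 8 example in Section 6.2.2.4 is a separate minor wording point that could be tidied in the same amendment.

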**Table 6-6. AMG 340 Dose Modification Guidelines for Adverse Events**

Grade	Interruption/ Delay	Specific Management	Re-start Guidance	Permanent Discontinuation
Gastrointestinal events related to AMG 340				
2	Interruption/delay required if deemed intolerable by the subject or investigator and not responding to appropriate medical management until event has improved to grade $\leq 1$	Gastrointestinal (GI) toxicities should be managed according to the local standard of care and institutional guidelines	
 
Re-start possible if successfully managed and improvement to <math>\leq</math> grade 1 in <math>\leq</math> 14 days.
 
Delay of next infusion: 
 
<math>\leq</math> 7 days: Administer the delayed infusion (as long as the next scheduled infusion is <math>></math> 6 days from delayed infusion) and follow the schedule of assessments for the cycle day on which the infusion was originally planned.
 
<math>></math> 7 days: Skip the delayed infusion and resume schedule of assessments for the next scheduled infusion
 
 
 
Hospitalization: 48 hours
 
Dose modification: Resume at the same dose or reduce to next lower dose if clinically indicated
 
	If subject missed more than 2 consecutive doses of AMG 340

Page 11 of 19

Abbreviations and footnotes defined on last page of table.

